589 computer based system with secure allocation concealment that cannot be changed once allocated, and will allocate the
590 paramedics in a 1:1 ratio to the two groups.

591

592 Randomisation will be carried out by a member of the CTEU Bristol, or appropriately trained member of the research
593 team.

594

595 Code breaking will not be necessary since paramedics will be aware of their allocation, and whilst the intervention is in
596 progress the allocated treatment will be apparent. Furthermore, once the intervention has been completed subsequent
597 in-hospital treatment is not influenced by study allocation.

598

599 **5.2 Procedures to minimise bias**

600

601 **5.2.1 Selection/allocation bias**

602

603 First, established objectively defined criteria will be used by participating paramedics to determine whether a
604 resuscitation attempt is appropriate, and hence whether the patient is eligible (see standardised resuscitation guidelines,
605 section 4.4.2).

606

607 Second, we will institute a programme of regular monitoring by analysing the proportion of cardiac arrests recruited, to
608 detect any imbalances that may be caused by different thresholds for resuscitation. We will also monitor the presenting
609 rhythm, proportion of witnessed and un-witnessed arrests, presence of bystander CPR and time from 999 call to crew
610 arrival.

611

612 If we suspect that a different threshold for resuscitation is being applied by one or more paramedics participating in the
613 trial, the first step will be to identify the personnel involved and ensure that their training in the trial procedures is up to
614 date, and reinforce the essential messages about the rationale for the trial. The trial team will include a local research
615 paramedic in each of the 4 ambulance regions, this person will develop a close working relationships with the
616 participating paramedics, and will be ideally placed to undertake this role.

617

618 **5.2.2 Blinding**

619

620 Because of the nature of the intervention, ambulance clinicians cannot be blinded, and will be aware of treatment
621 allocations, with an attendant risk of performance bias. However control room personnel will be blinded to the
622 allocation of paramedics, and follow established protocols when allocating resources to a possible cardiac arrest. This
623 will ensure that there is no bias in despatch.

624

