910

911 A detailed analysis plan will be prepared and agreed with the DMSC before the database is locked and any
912 comparisons between groups are investigated.

913

914 Non-adherence to allocated group will be documented. The trial will be analysed on an intention-to-treat basis, i.e.
915 outcomes will be analysed according to the treatment allocation, irrespective of future management and events, and
916 every effort will be made to include all participants treated by a study paramedic who meet the inclusion criteria.
917 Follow-up for the outcomes measures during the participant's stay in hospital and at the 3 month and 6 month window
918 should be complete for all participants that consent to taking part in the study.

919

920 **6.2 Subgroup analyses**

921

922 Two sub-group analyses are planned: the Utstein comparator group (estimated to make up about 20% of the total) vs.
923 non-comparator group, and arrest witnessed by ambulance staff (estimated to make up 6% of the total) or not. We will
924 describe the outcomes in the sub-groups and test for differences in the primary outcome between subgroups by
925 including interaction terms in the models, although we recognise that the power to detect such differences will be low
926 as the proportions in the subgroups will be unequal.

927

928 **6.3 Frequency of analyses**

929

930 The primary analysis will take place when follow-up is complete for all recruited participants. Formal interim analysis
931 is planned at the mid-point of recruitment (after 12 months), and will be presented to the DMSC. Safety data will be
932 reported together with any additional analyses the committee request. In these reports the data will be presented by
933 group but the allocation will remain masked.

934

935 **6.4 Criteria for the termination of the trial**

936

937 The trial may be terminated early on the instruction of the trial steering committee (TSC) when following
938 recommendations from the DMSC or if an interim analysis of the data from this trial or the results of another study
939 supersede the necessity for completion of this study.

940

941 The trial will also be stopped prematurely if mandated by the Research Ethics Committee (REC) or if funding for the
942 trial ceases.

943

944 The REC will be notified in writing if the trial has been concluded or terminated early.

945

946 **6.5 Economic evaluation**
947

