- **Population 0:** The population of patients who were resuscitated but did not become trial patients (either because they were not attended by an A2 paramedic or were ineligible). Characteristics of this population will be compared to those in population 1 (see **Table 1**).

1821 The primary analysis will be performed on an ITT basis, with patients grouped by the allocation of their first
1822 A2 paramedic on scene (see section 6.2.2 for details).

1823 **3.8 Safety population**

1824 The safety population is all trial patients (cf. analysis population for the primary outcome). Only serious
1825 adverse events which are unexpected and related to the intervention are collected, so numbers are expected to
1826 be low. These will be presented along with all intervention details.

1827

1828 **4. DATA SOURCES**

1829 A number of variables collected in AIRWAY-2 are recorded in more than one place. The following table details
 1830 these variables and identifies the primary data sources and the order in which data will be selected; for example
 1831 gender will be taken from Form G2, if not available from Form G2 then Form G will be used, if not available
 1832 from Form G then Form E1 will be used and if not available from Form E1 then Form B will be used.

Variable	Data sources	Order of preference
Date and time of incident	Form A (CAD) Form E1 (paramedic)	Always use form A as this should be available for all patients
Gender	Form B (minimal dataset/CAD) Form E1 (paramedic) Form G (hospital details, only available for those surviving to hospital admission)	1. Form G2 2. Form G 3. Form E1 4. Form B
Date of birth (DOB)	Form B (minimal dataset/CAD) Form E1 (paramedic) Form G (hospital details, only available for those surviving to hospital admission)	1. Form G2 2. Form G 3. Form E1 4. Form B
Approximate age (Note. This variable will only be used if the date of birth is missing from all sources. If date of birth is recorded, age will be derived (see Section 5))	For patients who do not survive to hospital, age may be estimated on scene. If this is the case, this will be recorded on Form B (minimal dataset/CAD) Form E1 (paramedic)	1. Form E1 2. Form B
Presenting rhythm	Form B (minimal dataset/CAD) Form E1 (paramedic)	1. Form E1 2. Form B
Was event witnessed?	Form B (minimal dataset/CAD) Form E1 (paramedic)	1. Form E1 2. Form B
Who was the event witnessed by?	Form B (minimal dataset/CAD) Form E1 (paramedic)	1. Form E1 2. Form B

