Time to death event/censor variable	
If (survival status≠survived to 30 days/hospital discharge & survival status≠missing) or has patient died since hospital discharge=Yes, then = 0
 
If survival status=survived to 30 days/hospital discharge & (has patient died since hospital discharge=No or missing), then = 1
 
Else missing
 
Note – if time to death exceeds 183 days, then it will be censored at 183 days

72 hour survival	
if time to death≥72 hours, then = Yes
 
if time to death<72 hours & time to death censor variable=0, then = No
 
if time to death<72 hours & time to death censor variable=1 & (mRS date-incident date) >3 & mRS at 30 days/discharge≠6, then = Yes
 
Else missing

Time to death: 0 to 72h	
if time to death≥72 hours, then = 72h
 
if time to death<72 hours & time to death censor variable=0 (patient died), then = time to death

New variable	Rules
	if time to death < 72 hours & time to death censor variable = 1 (censored) & ((30 day/discharge mRS date - incident date) > 3 & mRS at 30 days/discharge ≠ 6), then = 72h
	if time to death < 72 hours & time to death censor variable = 1 (censored) & ((30 day/discharge mRS date - incident date) ≤ 3 & mRS at 30 days/discharge ≠ 6), then = time to death
	Else missing
Time to death event/censor variable: 0 to 72h	if time to death ≥ 72 hours, then = 1 if time to death < 72 hours & time to death censor variable = 0 (patient died), then = 0 if time to death < 72 hours & time to death censor variable = 1 (censored), then = 1 Else missing
First crew arrival to first A2 paramedic arrival (mins)	(First A2 arrival date - First crew arrival date) * 24 * 60 + (First A2 arrival time - First crew arrival time)
Time of 999 call to first A2 paramedic arrival (mins)	(First A2 arrival date - Incident date) * 24 * 60 + (First A2 arrival time - Incident time)
Time between incident and discharge/30 day mRS measurement (days)	(mRS date - incident date) if measured face-to-face Else missing
Event witnessed by	if event witnessed by = non-ambulance staff (Form E1) or (event witnessed by = missing (Form E1) and event witnessed by = bystander (Form B)), then = bystander If event witnessed by = AIRWAYS-2 paramedic or ambulance staff (Form E1) or (event witnessed by = missing (Form E1) and event witnessed by = EMS (Form B)), then = EMS Else missing

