Utstein comparator group	if event witnessed by = bystander and presenting rhythm = VF or pulseless VT, then = Yes if (event witnessed by = bystander and presenting rhythm = Asystole OR PEA OR unknown) or event witnessed by = EMS, then = No Else missing
Protocol deviation 1: consciously enrolled but ineligible	if consciously enrolled = Yes AND trial patient = No, then = Yes if trial patient = Yes, then = No Else missing
Protocol deviation 2: wrong paramedic enrolling patient	if Paramedic AIRWAYS-2 ID (Form A) ≠ Paramedic AIRWAYS-2 ID (Form E1) and Paramedic AIRWAYS-2 ID (Form E1) ≠ missing and trial patient = Yes, then = Yes if Paramedic AIRWAYS-2 ID (Form A) = Paramedic AIRWAYS-2 ID (Form E1) and Paramedic AIRWAYS-2 ID (Form E1) ≠ missing and trial patient = Yes, then = No
Protocol deviation 2: wrong paramedic enrolling patient resulting in allocation crossover	if protocol deviation 2 = Yes and allocation of enrolling paramedic ≠ allocation of first A2 paramedic on scene, then = Yes if protocol deviation 2 = Yes and allocation of enrolling paramedic = allocation of first A2 paramedic on scene, then = No Else missing
Protocol deviation 3:	if 'If no [airways management attempt completed on CRF E2], why?' = Further airway management commenced once A2 paramedic arrived but not carried out by enrolling A2 paramedic and trial patient = Yes, then = Yes

New variable	Rules
	if 'has at least one airway management attempt recorded on CRF E2?' ≠ missing and 'If no [airways management attempt completed on CRF E2], why?' ≠ Further airway management commenced once A2 paramedic arrived but not carried out by enrolling A2 paramedic and trial patient = Yes, then = No Else missing
Protocol deviation 4	if (Paramedic allocated to i-gel and first advanced airways management attempt is intubation or other SGA) or (Paramedic allocated to intubation and first advanced airways management attempt is i-gel or other SGA and paramedic is not a solo responder), then = Yes if first advanced airway management attempt matches paramedic allocation, then = No Else missing (including patients with no advanced airways management attempts)

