1940 the best fit in terms of information criteria such as AIC, BIC and likelihood ratio tests will be used.

1941 **6.2.3 Statistical significance**

- 1942 For hypothesis tests two-tailed p-values < 0.05 are considered statistically significant.
- 1943 **6.2.4 Model assumptions**
- 1944 For all methods outlined underlying assumptions will be checked using standard methods, e.g. residual plots,
1945 tests for proportional hazards, etc. If assumptions are not valid then alternative methods of analysis will be
1946 sought. If outlying observations are found which mean models do not fit the data adequately, such
1947 observations will be excluded from the main analyses and comments made in footnotes.
- 1948 **6.2.5 Subgroup analyses**
- 1949 Two subgroup analyses for the primary outcome are specified in the protocol: Utstein comparator group vs
1950 non-comparator group and arrest witnessed by ambulance staff or not (**Figure F7**).
- 1951
- 1952 Due to concerns regarding ventilation success raised during the trial, a subgroup analysis of the primary
1953 outcome comparing patients whose i-gel or intubation airway management attempt(s) were or were not
1954 ‘successful’ during the first and/or second attempt (see section 5.2 for definition) will also be performed. This
1955 analysis will be performed per-protocol and as such will only include patients who received at least one
1956 advanced airway management attempt using an i-gel and/or intubation tube.
- 1957
- 1958 Subgroup effects will be fitted by adding a “sub-group x intervention” interaction term to the analysis model.
- 1959 **6.2.6 Sensitivity analyses**
- 1960 For the primary outcome, the following sensitivity analyses will be performed:
- 1961
 - ITT analysis including only patients who received at least one advanced airway management attempt
1962 using an i-gel and/or intubation tube.
 - Per-protocol analysis including only patients who received at least one advanced airway management
1963 attempt using an i-gel and/or intubation tube (see section 6.2.5 for additional sub-group analysis for
1964 this outcome).
 - ITT analysis including all patients who were attended by an AIRWAYS-2 paramedic but not
1965 resuscitated.
- 1966
- 1967
- 1968 **6.2.7 Missing data**
- 1969 In all tables missing data will be indicated by footnotes. If the amount of missing data differs substantially
1970 between treatment groups potential reasons will be explored.
- 1971 Missing predictors:

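### As written, the Utstein subgroup rule sets arrests recorded as unwitnessed to missing, although they are known not to be in the comparator group

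*Protocol*

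**What the plan says.** Protocol section 6.2 plans two subgroup analyses. The first is "the Utstein comparator group (estimated to make up about 20% of the total) vs" the non-comparator group; the second is arrests witnessed by ambulance staff, put at 6% of the total, against the rest. SAP section 6.2.5 carries both over for the primary outcome ("non-comparator group and arrest witnessed by ambulance staff or not") and tests each by adding a subgroup-by-intervention interaction term to the model.

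SAP section 5.4 derives the variables. The witness variable is bystander or EMS, taken from Form E1 with Form B as back-up, and its last line is "event witnessed by = EMS (Form B)), then = EMS Else missing". The Utstein variable is then built on it:

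- Yes: "if event witnessed by = bystander and presenting rhythm = VF or pulseless VT, then = Yes".
- No: a bystander witness with a rhythm of "Asystole OR PEA OR unknown) or event witnessed by" EMS. With the fallback, the text runs "presenting rhythm = Asystole OR PEA OR unknown) or event witnessed by = EMS, then = No Else missing".

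SAP section 4 also lists a separate item, "Was event witnessed", with its own order of sources. Neither derivation uses it.

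**The concern.** The witness variable has no unwitnessed level. An arrest that is recorded as seen by nobody has no value for it, cannot satisfy either Utstein branch, and is left as missing. Its status is not unknown, however: under the SAP's own rule a comparator must have a bystander witness, so an unwitnessed arrest is a non-comparator whatever its rhythm.

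The trial expects such patients. Protocol section 5.2.1 lists, among the characteristics to be monitored, "rhythm, proportion of witnessed and un-witnessed arrests, presence of bystander CPR and time from 999 call to crew" arrival. No section says that they are to be left out of the subgroup analysis.

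At stake is what the subgroup result means. The comparator stratum would be as planned, but the other stratum would contain witnessed arrests only, and the interaction test would compare the comparator group with something other than its complement.

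**Working it through.** **1. Every combination under the rule as written**

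| Derived witness value | VF or pulseless VT | Asystole, PEA or unknown | Rhythm blank |
|---|---|---|---|
| Bystander | Yes | No | missing |
| EMS | No | No | No |
| No value (includes unwitnessed) | missing | missing | missing |

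No path returns No for an arrest without a witness value. The rule does return No for a bystander-witnessed arrest of unknown rhythm, so it classifies a patient about whom less is known while leaving a known non-comparator unclassified. In the same section, the variable for loss of an established airway does use its parent item: an attempt with no ventilation success counts towards No. The equivalent step is absent here.

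**2. Whether another rule repairs it**

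SAP section 6.2.7 deals with randomisation factors and with missing outcomes. It gives no rule for a missing subgroup variable. A standard fit of the interaction model drops patients who lack that variable.

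**3. The denominator**

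Inputs from protocol section 4.7: 8% against 10%, 5% level (taken as two-sided), 90% power, ICC 0.005, 7 patients per paramedic.

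- The two-proportion formula gives 4,301 per group without and 4,401 with continuity correction, against 4,400 stated.
- Design effect: 1 + (7 − 1) × 0.005 = 1.03. Then 4,400 × 1.03 = 4,532, against 4,535 stated.

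The plan's figure is reproduced to within rounding, and 2 × 4,535 = 9,070 is used below.

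**4. The split the protocol intends**

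- Comparator: 0.20 × 9,070 = 1,814.
- Non-comparator: 0.80 × 9,070 = 7,256.

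**5. What the documents say about the unwitnessed share**

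They give no figure. Comparator (20%) and EMS-witnessed (6%) do not overlap, so all others make up 100 − 20 − 6 = 74%. That remainder also holds bystander-witnessed arrests with other rhythms, so 74% is a ceiling and not an estimate.

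**6. Size for an assumed unwitnessed share u**

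Set to missing = u × 9,070. Non-comparators left = (0.80 − u) × 9,070. Share of non-comparators lost = u / 0.80. Comparator share of those classified = 0.20 / (1 − u).

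| u (assumed) | Set to missing | Non-comparators left (of 7,256) | Share of non-comparators lost | Comparator share of those classified |
|---|---|---|---|---|
| 10% | 907 | 6,349 | 12.5% | 22.2% |
| 30% | 2,721 | 4,535 | 37.5% | 28.6% |
| 50% | 4,535 | 2,721 | 62.5% | 40.0% |
| 74% (ceiling) | 6,712 | 544 | 92.5% | 76.9% |

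The whole loss falls on the non-comparator side.

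**The case against.** The best defence is that this is a drafting gap in a low-power secondary analysis. Protocol section 6.2 already concedes low power for both subgroup tests. The primary analysis does not use the variable, and the comparator stratum is classified completely apart from blank rhythms. All of that stands, and it limits how serious the point is. It does not make the rule correct.

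Several stronger readings are tempting, and the documents do not support them:

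- *That a large share of the trial is lost.* The unwitnessed proportion is nowhere stated, so only the conditional figures can be given.
- *That the loss would be silent.* SAP section 6.2.7 requires footnotes for missing data in tables, and skeleton Table T4 reports witnessed status by arm, so a shortfall could be noticed. A footnote would still describe known non-comparators as missing.
- *That the estimate is biased in a known direction because these patients do badly.* The documents give no prognosis for unwitnessed arrests.
- *That the ambulance-witnessed subgroup loses the same patients.* The SAP does not say that this subgroup is built from the two-level witness variable. Both source items are listed in section 4 and could be used directly. The loss occurs there only if the derived variable is used without recoding.
- *That every unwitnessed arrest is affected.* If the witness field on Form E1 is blank and Form B says bystander, the patient is classified as bystander-witnessed.

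**Conclusion.** The point holds for the Utstein variable. As written, the rule returns missing for arrests recorded as unwitnessed, which contradicts the contrast set out in protocol section 6.2 and SAP section 6.2.5, and nothing elsewhere in the SAP corrects it. The coding error follows from the text alone. Its size does not: the patient counts rest on the assumed unwitnessed share, on the planned total of 9,070, and on the protocol's own 20% and 6% estimates. Even at 10% unwitnessed, one-eighth of the non-comparator group would drop out.

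A reader might infer that the trial's main result is at risk. It is not: the primary intention-to-treat analysis and the sample size are untouched. This is an error that should be fixed in one pre-specified subgroup analysis of the primary outcome, not a threat to the trial's conclusions.

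**What to change.** In SAP section 5.4, extend the Utstein No branch so that it also applies when the item on whether the event was witnessed equals No. Keep missing for genuinely unknown witness status, and for a bystander-witnessed arrest whose rhythm was not recorded. After coding, check that Yes, No and missing add up to Population 1a and that no patient recorded as unwitnessed remains among the missing.

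If the two-level witness variable is also used for the ambulance-witnessed subgroup, code unwitnessed arrests there as not witnessed by ambulance staff.

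The cost is one line in the derivation table, the matching line of code and an entry in the SAP amendment log. No new data are needed, since the item is already collected on Forms E1 and B.

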1643 with **Appendix A**.

1644

1645 **2. STUDY BACKGROUND AND OBJECTIVES**

1646 **2.1 Study background**

1647 AIRWAYS-2 is a randomised controlled trial (RCT) in four UK ambulance trusts (South Western Ambulance
1648 Service NHS Foundation Trust (SWAST), East of England Ambulance Service NHS Trust (EAST), East
1649 Midlands Ambulance Service NHS Trust (EMAS) and Yorkshire Ambulance Service NHS Trust (YAS)) with
1650 cluster randomisation at the paramedic level.

1651 Two advanced airway management devices for the treatment of out of hospital cardiac arrests (OHCA) are
1652 compared: the i-gel, a second generation supraglottic airway device (SGA), and tracheal intubation, currently
1653 standard practice.

1654 Ambulance staff performing the airway management are unable to be blinded to allocation but the patients
1655 and research staff assessing all outcomes post hospital admission (including the primary outcome) will be
1656 blinded.

1657 **2.2 Study objectives**

1658 1. To estimate the difference in the primary outcome of mRS at hospital discharge or 30 days post OHCA,
1659 whichever comes first, between groups of patients managed by paramedics randomised to use either the i-gel
1660 or intubation as their initial advanced airway management strategy following OHCA.

1661 2. To estimate differences in secondary outcome measures relating to airway management, hospital stay and
1662 recovery at 3 and 6 months between groups of patients managed by paramedics randomised to use either the i-
1663 gel or intubation.

1664 3. To estimate the comparative cost effectiveness of the i-gel and intubation, including estimating major in
1665 hospital resources and subsequent costs (length of stay, days of intensive and high dependency care, etc.) in
1666 each group. This objective will not be covered in this analysis.

1669 **2.3 Primary outcome**

1670 The primary outcome is mRS assessed at hospital discharge (or 30 days post OHCA if patient remains in
1671 hospital until this time). The mRS incorporates survival status and will be analysed as good recovery (scores 0
1672 to 3) compared to poor recovery/death (scores 4 to 6).

1673 **2.4 Secondary outcomes**

1674 The protocol includes the secondary outcomes listed below (a health economic outcome is also listed in the
1675 protocol but excluded here).

1676 All enrolled patients:

- 1677 1. Initial ventilation success, defined as visible chest rise and end tidal carbon dioxide (ETCO₂) at the first

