1678 or second attempt¹.
- 1679 2. Regurgitation/aspiration.
- 1680 3. Loss of a previously established airway.
- 1681 4. Actual sequence of airway interventions delivered.
- 1682 5. Chest compression fraction (two ambulance regions only, added part way through the trial)
- 1683 6. Return of spontaneous circulation (ROSC)*.
- 1684 7. Airway management in place when first ROSC was achieved or the resuscitation was discontinued.
- 1685

1686 Patients who survive to admission to hospital (estimated 20% of enrolled patients):

- 1687 8. Length of intensive care stay.
- 1688 9. Length of hospital stay.

¹ Note: chest rise and ETCO₂ is the definition on the CRF, but ETCO₂ is not included in the definition given in the protocol. Also, the protocol does not state whether success should be based on the first attempt only or the first or second attempt.

1689	
1690	Patients who survive to hospital discharge and consent to active follow-up (estimated 9% of enrolled
1691	patients):
1692	10. Quality of life (using the EQ-5D) at hospital discharge.
1693	
1694	Patients who survive beyond hospital discharge and consent to active follow-up:
1695	11. Time to death or last follow-up
1696	12. Modified Rankin score at 3 and 6 months following OHCA
1697	13. Quality of life (using the EQ-5D) at 3 and 6 months following OHCA.
1698	* note: this outcome includes both ROSC during advanced airway management attempts carried out by an
1699	AIRWAYS-2 paramedic and on ED arrival for those patients conveyed to ED
1700	2.5 Changes to the study objectives during the course of the study
1701	N/A
1702	2.6 Changes to the study outcomes during the course of the study
1703	There have been no outcomes added or removed, but outcomes that were not clearly defined in the protocol
1704	have been reviewed and precise definitions have been agreed. These include definitions for secondary
1705	outcomes 1 to 7, the addition of time to death as a more informative means of comparing length of ICU and
1706	hospital stays and two analyses of survival at 72h (as binary and time to event outcomes) . Definitions are
1707	given in Section 5.
1708	

1709 **3. STUDY POPULATION**

1710 The study population is patients aged 18 or over experiencing a non-traumatic OHCA. Enrolled patients must
1711 be attended by an A2 paramedic who is first or second at the patient's side and resuscitation must be

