	
If ventilation success= yes on first other SGA attempt, then = Yes
 
If ventilation success = no on the first other SGA attempt and the next advanced attempt is also other SGA and on that attempt ventilation success = yes, then = Yes
 
If ventilation success = no on first other SGA attempt and the next advanced attempt is also other SGA and ventilation success = no, then = No
 
If ventilation success = no on first other SGA attempt and (there is no further attempt or the next advanced attempt is i-gel or intubation), then = No
 
Else missing

Any ventilation success	
If ventilation success=Yes for any advanced airway management attempts on Form E2, then = Yes
 
If ventilation success=No for all advanced airway management attempts on Form E2, then = No
 
Else missing

Any loss of previously established airway (only calculated if any ventilation success=Yes)	
If 'if an airway was established, was it later lost'=Yes for any advanced airway management attempts on Form E2, then = Yes
 
If ('if an airway was established, was it later lost'=No OR 'ventilation success'=No) for all advanced airway management attempts on Form E2, then = No
 
Else missing

Actual sequence of airway interventions delivered	
If at least one airway management attempted:-
 
A six digit code will be derived from the airway management type (1=OPA, 2=NPA, 3=i-gel, 4=intubation, 5=other SGA, 6=other) used at the first to the 6th airway management attempt, using the following:
 
Code = 100000*1st attempt airway management type + 10000*2nd attempt airway management type + 1000*3rd attempt airway management type + 100*4th attempt airway management type + 10*5th attempt airway management type + *6th attempt airway management type
 
If no airways management attempted, = missing

Any ROSC during airway management	
If 'was ROSC achieved'=Yes for any advanced airway management attempts on Form E2, then = Yes
 
If 'was ROSC achieved'=No for all advanced airway management attempts on Form E2, then = No
 
Else missing

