Airway management in place when first ROSC was achieved or the resuscitation was discontinued if no ROSC was achieved	
if ('any ROSC achieved during airway management'=Yes and airway management first time ROSC was achieved=intubation) OR ('any ROSC achieved during airway management'=No and final airway attempt=intubation and 'was airway management handed over'=No), then = intubation
 
if ('any ROSC achieved during airway management'=Yes and airway management first time ROSC was achieved= i-gel) OR ('any ROSC achieved during airway management'=No and final airway attempt= i-gel and 'was airway management handed over'=No), then = i-gel

New variable	Rules
	
if ('any ROSC achieved during airway management'=Yes and airway management first time ROSC was achieved= any SGA) OR ('any ROSC achieved during airway management'=No and final airway attempt= any SGA and 'was airway management handed over'=No), then = other SGA if ('any ROSC achieved during airway management'=Yes and airway management first time ROSC was achieved=OPA/NPA) OR ('any ROSC achieved during airway management'=No and final airway attempt= OPA/NPA and 'was airway management handed over'=No), then = other Else missing

POPULATION 3:	
Duration of initial ICU stay	
For patients who survive to ICU discharge in admitting hospital and (were not transferred or were transferred to another hospital but at a lower level of care) = (ICU discharge date - ICU admission date)*24*60 + (ICU discharge time - ICU admission time)
 
For patients who are transferred from ICU in the admitting hospital to ICU (level 3 care) in another hospital and survives to ICU discharge in the transferred hospital = ((ICU discharge date on Form G2 - ICU admission date on Form G)*24*60 + (ICU discharge time on Form G2- ICU admission time on form G))
 
For patients who die in ICU in the admitting hospital (i.e. censored for analysis) = (ICU death date - ICU admission date)*24*60 + (ICU death time - ICU admission time)
 
For patients who are transferred from ICU in the admitting hospital to ICU (level 3 care) in another hospital and die in ICU in the transferred hospital (i.e. censored for analysis) = ((ICU death date on form G2 - ICU admission date on form G)*24*60 + (ICU death time on form G2 - ICU admission time on form G))

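### Secondary outcome 7 can record an airway that was not in place, because patients without ROSC are coded by the last device attempted, whether or not it worked

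*Protocol*

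**What the plan says.** SAP 2.4 lists secondary outcome 7 as "Airway management in place when first ROSC was achieved or the resuscitation was discontinued". SAP 2.6 says that definitions for outcomes 1 to 7 were agreed and are given in Section 5, so the derivation table in SAP 5.4 is the governing definition. It applies to Population 2, trial patients with at least one advanced attempt by the enrolling A2 paramedic (SAP 3.7).

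Each branch of the rule has two limbs, one for patients with ROSC and one for patients without. The limbs without ROSC read:

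- Intubation: "any ROSC achieved during airway management'=No and final airway attempt=intubation and 'was airway management handed over'=No), then = intubation".
- i-gel: "any ROSC achieved during airway management'=No and final airway attempt= i-gel and 'was airway management handed over'=No), then = i-gel".
- Third branch: "final airway attempt= any SGA and 'was airway management handed over'=No), then = other SGA". Its limb with ROSC has the same condition: "airway management first time ROSC was achieved= any SGA".
- A fourth branch sends OPA/NPA to the category for other airways, and anything left is missing.

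The ROSC flag is derived just above in the same table: "If 'was ROSC achieved'=Yes for any advanced airway management attempts on Form E2, then = Yes". It is No when every advanced attempt has ROSC recorded as No.

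SAP 2.1 describes the devices as "compared: the i-gel, a second generation supraglottic airway device (SGA), and tracheal intubation, currently". The airway-sequence variable in SAP 5.4 keeps the types apart: "1=OPA, 2=NPA, 3=i-gel, 4=intubation, 5=other SGA, 6=other".

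SAP 6.1 and footnote 1 to the outcome table in SAP 6.2.2 state that this outcome is described without formal comparison.

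**The concern.** The label promises the airway that was in place. The limb without ROSC returns the airway that was last tried. These differ whenever the last attempt did not establish an airway, or established one that was then lost. SAP 5.4 draws this distinction elsewhere: the variables for any ventilation success and for loss of an established airway both use attempt-level items from Form E2.

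The error need not cancel between arms. Protocol 9.3 says that misplacement is possibly more common with intubation and dislodgement possibly more common with the i-gel. SAP 6.2.5 adds a subgroup analysis because ventilation success became a worry during the trial.

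What is at stake is whether a listed secondary outcome measures what its name says, and whether two programmers working from SAP 5.4 would produce the same table.

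**Working it through.** No figure in the plan needs reproducing; the check is to run the rule as printed over every kind of record.

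**Inputs, all from SAP 5.4:** the ROSC flag (Yes/No), the six airway types in the sequence variable, success of the attempt (Yes/No), and handover (Yes/No, which matters only without ROSC).

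**Number of cells:** with ROSC, 6 × 2 = 12. Without ROSC, 6 × 2 × 2 = 24. Total 36, or 18 pairs that differ only in success.

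**1. Success.** The assigned code is the same in both members of all 18 pairs. For example, after two failed intubation attempts with no further device, no ROSC and no handover, the record is coded as intubation in place. Later loss is not an input to the rule, so it cannot change the code either.

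**2. ROSC flag.** Take ROSC with an OPA, then an i-gel with no further ROSC, and no handover. The flag looks only at the i-gel attempt and is No. The record enters the limb without ROSC and is coded by its last device, the i-gel. On the outcome's own label the answer is the OPA, the airway at first ROSC. This takes the flag named in the rule to be the variable defined just above it; the names differ by one word, but SAP 5.4 defines no other. Table T7 has separate rows for ROSC during advanced and during any A2 airway management, so the wider quantity is already foreseen.

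**3. SGA branch.** Because the i-gel is an SGA, an i-gel record meets both the i-gel branch and the third branch. This happens in 4 of the 36 cells: 2 with ROSC, and 2 without ROSC and without handover.

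| Reading of the branches | Code for these i-gel records |
|---|---|
| First match wins | i-gel (correct) |
| Later lines overwrite earlier ones | other SGA (wrong, every such record) |

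The SAP states neither reading. Every other airway type meets at most one branch.

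**The case against.** The strongest reply is that this is a descriptive row and the basis is partly disclosed. Table T7 labels the related rows by the final attempt of the A2 paramedic, and the outcome table in SAP 6.2.2 adds the point at which that paramedic's intervention stopped. A recorded fallback to an OPA or NPA is captured, because the final attempt is not limited to advanced devices. Conditioning on success also has a price: the SAP 2.4 footnote gives the CRF definition of success as chest rise plus ETCO2, so a device physically present without both would count as not established. These points stand. They limit the importance and make relabelling an acceptable minimum. They do not settle the matter, since the T7 labels still say the airway was in place and SAP 2.4, 5.4, 6.2.2 and T7 describe the endpoint differently.

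Four stronger readings are tempting but not supported:

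- **That i-gel records are miscoded.** That requires an overwriting order that the SAP does not state. The separate type codes and the value assigned suggest that other SGA was meant.
- **That the OPA/NPA branch for first ROSC can never be reached.** It can: ROSC with an OPA, re-arrest, then ROSC during an advanced attempt sets the flag to Yes.
- **That device failure is hidden.** Table T7 reports initial success, any success and any loss by device.
- **That the outcome is used to interpret the mRS result or crossover.** Neither document says so. Crossover is handled by the protocol-deviation variables, and the per-protocol analyses use the first advanced airway.

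**Conclusion.** The point holds as a defect of definition in a descriptive secondary outcome. Followed exactly, SAP 5.4 can report a failed or lost final attempt as the airway in place, and can treat a patient whose only ROSC came with an OPA/NPA before an advanced attempt as having had none. Both follow from the text; the second assumes that the rule uses the ROSC flag SAP 5.4 defines. The SGA overlap is a wording fault that does harm only if later branches overwrite earlier ones.

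The size cannot be derived. A count per arm would need the shares of patients with an advanced attempt, without ROSC, without handover, and with a failed or lost final attempt. The documents supply none of these for this purpose, and multiplying guesses by the planned 4,535 per group would only return the guesses. The first problem is confined to patients without recorded ROSC and without handover. The primary outcome and all formal comparisons are unaffected, so the importance is low, but the correction is cheap.

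**What to change.** In SAP 5.4, for this variable only:

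1. In the limb without ROSC, code the final attempt as in place only if ventilation success is Yes and later loss is not Yes on that attempt. Otherwise assign a new category, not established. The SAP shows these items in use for advanced attempts; check whether Form E2 also holds them for OPA/NPA. At minimum, relabel the limb as last airway attempted.
2. Define ROSC over all A2 airway attempts, as in the existing wider row of Table T7. Leave the ROSC outcome that is formally compared as it is.
3. Change the third branch, in both limbs, to other SGA (not i-gel), and state that the branches are mutually exclusive.
4. Align the wording of the endpoint in SAP 2.4, 5.4, 6.2.2 and Table T7.

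The cost is SAP wording, code and one extra category in Table T7. The full version relies on items the SAP already takes from Form E2 for advanced attempts; no new data collection is needed for those.
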